3.3.4 Handling of Unscheduled Visits

Any data collected at early discontinuation and unscheduled visits will be listed and included in the definition of maximum/minimum value. The Early Discontinuation and Unscheduled visits will be included when applying the visit windows to ensure that all available data are used in the analysis.

3.3.5 Multiplicity/Multiple Comparisons

No multiplicity/multiple comparison are planned for this study.

3.3.6 Handling of Protocol Deviations in Study Analysis

The deviations from the protocol will be classified as important or non-important by blinded members of the study team.

The list of study specific IPDs is provided in the AstraZeneca Protocol Deviations Plan (PDP). Refer to the PDP for all details of IPDs. Important deviations will include the following:

- Inclusion criteria deviations
- Exclusion criteria deviations
- Discontinuation criteria for study treatment met but participant not withdrawn from study treatment
- Discontinuation criteria for overall study withdrawal met but participant not withdrawn from study
- Investigational product deviation
- Excluded medications taken
- Deviations to study procedure
- Other important protocol deviations

Additionally, all protocol deviations and major issues related to COVID-19 (such as missed visit, procedure not performed at visit etc.) will be captured with the prefix "COVID19" for CSR reporting.

All important protocol deviations except for dosing error will be identified and documented by the study team prior to unblinding of the trial.

Prospective approval of protocol deviations to recruitment and enrolment criteria, also known as protocol waivers or exemptions, is not permitted.

3.4 General Principles and Analysis Methods

Efficacy analyses will be performed using the FAS. Demography and baseline characteristics will be summarised by study intervention group for the FAS. Safety analyses will be performed on SS.

Study intervention groups will be displayed as follows:

- AZD4831
- Placebo

A column reflecting all participants ("Total") will be included in tables that summarise study population data.

The below mentioned general principles will be followed throughout the study:

- Descriptive statistics will be used for all variables, as appropriate. Continuous variables will be summarised by the number of observations, mean, SD, median, upper and lower quartiles, minimum, and maximum. For log-transformed data geometric mean, CV%, median, minimum and maximum will be presented. Categorical variables will be summarised by frequency counts and percentages for each category.
- Concentration data will be summarised using descriptive statistics, including n, n<LLOQ, geometric mean, CV%, arithmetic mean, SD, minimum, median, and maximum values. The geometric mean is calculated as the exponential of the arithmetic mean calculated from data on a log scale.
- Unless otherwise stated, percentages will be calculated out of the population total for the corresponding study intervention group. Overall totals will be calculated for baseline summaries only.
- For continuous data, the mean and median will be rounded to 1 additional decimal place compared to the original data. The SD will be rounded to 2 additional decimal places compared to the original data. Minimum and maximum will be displayed with the same accuracy as the original data. CV%, where reported, will always be reported to 1 decimal place.
- PK concentration data will be presented in the listings to the same number of significant digits as the data received from the bioanalytical laboratory (usually to 3 significant figures) and against the same units as received. PK concentration descriptive statistics will all be presented to 1 additional significant figure than original data. Min, max will be presented as original data, n and n<LLOQ which will be presented as integers.
- For categorical data, percentages will be rounded to 1 decimal place.
- SAS® version 9.3 (as a minimum) will be used for all analyses.

3.4.1 Time to event analysis

Time to event endpoints will be analysed using Kaplan-Meier survival analysis (PROC LIFETEST).

The following results at Weeks 4, 12, 18 and 24 will be reported by study intervention:

- The number of participants at risk
- the number of censored participants
- the number of events
- Kaplan-Meier estimates and CI

The Kaplan-Meier curves (active versus placebo) will be compared with a two-sided logrank test stratified by region.

Time to event endpoint will be displayed graphically using a Kaplan-Meier plot.

A Cox proportional hazard model stratified by region will be fitted with study intervention as covariate. If any regions have very few events (i.e. <10) the regions can be collapsed as appropriate. The Efron approximation will be used for any tied data. The hazards proportionality assumption of the model will be examined graphically using plots of complementary log-log (event times) versus log (time). If these raise concerns, the variation in treatment effect will be described by presenting piecewise hazard ratios calculated over distinct time-periods. The HR from the primary analysis will then represent the average HR, which can be potentially misleading and should be interpreted with caution (ref: Bartlett et al, 2020). Alternative analysis methods not assuming proportional hazard could also be considered, for example landmark analysis comparing Kaplan-Meier curves at a particular time point.

The reportable results for this model will be:

- hazard ratio estimate for the study intervention
- hazard ratio two-sided CI for the study intervention
- two-sided Wald test p-value for the hazard ratio

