6.3 Assignment to Study Intervention

All participants will be centrally assigned to randomised study intervention, and have an E-code assigned, using an Interactive Response Technology/Randomisation and Trial Supply Management (IRT/RTSM) system. Before the study is initiated, the log in information and directions for the IRT/RTSM will be provided to each site.

Participants will be randomised 1:1 to mitiperstat (AZD4831) 5 mg or placebo at SV3 (Table 1). Randomisation will be stratified by country.

Study intervention will be dispensed at the study visits summarised in the SoA (Table 1).

Returned study intervention should not be re-dispensed to the participants.

The IRT/RTSM will provide to the investigator(s) or pharmacists the kit identification number

to be allocated to the participant at the dispensing visit.

Routines for this will be described in the IRT/RTSM user manual that will be provided to each centre.

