9.4.2 Efficacy

9.4.2.1 Primary Endpoint

The primary endpoint to evaluate the clinical efficacy of mitiperstat (AZD4831) 5 mg compared with placebo is time to first COPDCompEx event. After at least 194 first COPDCompEx events have occurred, enrolment will be stopped and when the last participant completes 12 weeks of treatment, the study will stop (see Section 7.1.4). A logrank test and Cox's proportional hazards model will be used to analyse the time to first COPDCompEx event data. Survival probabilities will be presented as survival curves estimated using the Kaplan-Meier method. A two-sided logrank test P-value ≤ 0.10 is required to provide evidence of efficacy.

The primary estimand strategy for intercurrent events will be while on treatment and the supportive estimand strategy will be treatment policy (see Table 3). Model assumptions will be checked and mitigations for possible non-proportionality will be described in the SAP.

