3.3 General Considerations

Study design

This is a Phase IIa, randomised, placebo-controlled, double-blind, parallel-arm, event-driven study with an up to 24-week treatment time designed to evaluate the efficacy and safety of AZD4831 administered QD using a tablet in adult patients with confirmed moderate to severe symptomatic COPD (FEV1/FVC < 0.7, ≥ 10 pack-years smoking history, and post-BD FEV1 ≥ 25% predicted) who are at high risk of exacerbations despite being maintained on optimised SoC inhaled therapies - triple inhaled therapy (ICS/LABA/LAMA) or ICS/LABA dual therapy or LABA/LAMA dual therapy (for participants with a history of pneumonia or who are otherwise deemed unsuitable for ICS). The treatment will be over a minimum 12-week and maximum 24-week period. Further details about inclusion and exclusion criteria are available in Section 5 − Study population in the CSP.

Approximately 406 participants will be randomised 1:1 to AZD4831 QD or placebo QD. The randomisation will be stratified by country. The study will be blinded to both participants and investigators/site staff as well as to the sponsor.

The entire study period is planned to take between 18 and 30 weeks for each individual patient: a 4-week screening period, minimum 12 weeks to a maximum 24 weeks of dosing and 2 weeks of follow-up. The enrolment will be stopped after approximately 194 COPDCompEx events have occurred, and when the last enrolled patient completes 12 weeks of treatment, the study will stop. At the point the study ends due to the required number of COPDCompEx events occurring, participants who are receiving study intervention between Weeks 12 and 24 at the time the last patient completes Week 12 should attend SV7 as soon as possible, continuing treatment until they do. They should then attend SV8 14 ± 3 days

later. For further details and the Schedule of Activities, refer to Table 1 – Schedule of Activities in the CSP.

Study product

The study product is AZD4831 and it will be administered orally once a day as tablet containing 5 mg of investigational product (IP). The first dose of study intervention will be administered in clinic on the day of randomisation. Participants will receive study intervention at the site on visit days and at home between visits. No dose modification is allowed during the study.

Sample size determination

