3.4.3 Mixed Model Repeated Measures (MMRM)

The MMRM model will be used to fit change from baseline for continuous endpoints that have data at several post-baseline visits. The model will include all available data from all visits, irrespective of whether the patient discontinued study intervention. Since a repeated measures model is being applied, no imputation will be made for missing data. Region will be added as a random effect. The model will include fixed effects for baseline, visit, study intervention and the baseline by visit and study intervention by visit interactions. An unstructured covariance matrix will be used to describe the correlations on a patient between visits, and the Kenward-Roger correction will be used for degree of freedom approximation in the generation of the model. In the event that the model with unstructured covariance matrix fails to converge, an alternative such as autoregressive or compound symmetry will be used instead. Estimates of the least square (LS) mean change from baseline for each study intervention, and the difference between them (AZD4831-placebo), together with two-sided 90% CI, will be obtained from the model for each visit. The study intervention effect will be tested at the 10% two-sided level of significance.

The reportable results from the model are:

- The LSmeans change from baseline at each visit and their standard errors for each study intervention group.
- The difference in change from baseline at each visit between AZD4831 and placebo (LSmeans difference) together with its two-sided 90% confidence interval (CI).
- The two-sided p-value for the difference in change from baseline at each visit between AZD4831 and placebo.

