4.1.1.2 Presentation

Patient dispositions (number and percentage) of subjects enrolled, subjects not randomised (incl. reasons), subjects randomised, subjects randomised and who did not receive treatment, subjects who started treatment, subjects who completed the treatment, subjects who discontinued treatment (incl. reasons), subjects included in the cough substudy, subjects who completed the study and subjects withdrawn from study (incl. reasons) will be presented in a summary table for each study intervention group and overall. A listing including all standardised disposition terms will also be provided for all discontinued subjects and subjects completing the study. Both the table and the listings will be based on the screened set.

To demonstrate balance in stratification factor categories (i.e. countries), the number and percentage of participants in each category will be summarised by study intervention group and overall focusing on the randomised set.

The recruitment per country and site will be provided based on the screened set, while the global/country situation study disruption will be summarised on the full analysis set.

The number and percentage of participants with one or more disruption due to COVID-19 pandemic will be presented by study intervention group considering the participants valid for the full analysis set. A listing of all the participants affected by COVID-19 related study disruption will be produced by unique patient number identifier, investigational site, and a description of how the individual's participation was altered. COVID-19 related study disruptions can be:

- Visit related (if visit is impacted by global/country situation, then contact mode will be specified);
- Study drug related (if study drug action taken (except "Drug Withdrawn") was impacted by global/country situation; study drug administration or location was impacted by global/country situation; who performed a study drug administration);

- Discontinuation of study drug due to COVID-19 pandemic (if study drug action taken "Drug Withdrawn" was impacted by global/country situation);
- Withdrawal from study (if primary reason for ending study is related to global/country situation).

Randomisation scheme and codes as well as participants receiving the various batch of investigational product will also be listed for all randomised participants.

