4.2.1.4 Primary Analysis of Primary Endpoint

Kaplan-Meier curves, region-stratified logrank test and region stratified Cox proportional hazard (PH) model results, will be provided for time to first COPDCompEx event as specified in Section 3.4.1.

The evidence of efficacy requires a two-sided region-stratified logrank test p-value ≤ 0.10 .

Kaplan-Meier curve estimates will be provided with a 90% CI.

Survival probabilities will be presented as survival curves estimated using the Kaplan-Meier method.

Diagnostic plot (log-log) will be presented to assess proportional hazard assumption.

The hazard ratio estimate from the Cox PH model will be provided with a 90% CI.

COPDCompEx data will be listed.

The analyses will be focused on the FAS population, including only those subjects with post-baseline eDiary data.

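### Randomisation is stratified by country but the deciding log-rank test and Cox model only by region; the test stays valid but may be conservative and lose some power

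*SAP*

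**What the plan says.** Both documents name country as the randomisation stratum. Protocol 6.3: "Randomisation will be stratified by country". SAP 3.3: "The randomisation will be stratified by country". SAP 4.1.1.2 also treats countries as the stratification factor when it describes the balance table.

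The efficacy analysis uses a coarser grouping. Protocol 9.4.2.1 names no stratum: "A logrank test and Cox's proportional hazards model will be used to analyse the time to first COPDCompEx event data". SAP 3.4.1 then states that the survival curves "will be compared with a two-sided logrank test stratified by region", and adds: "A Cox proportional hazard model stratified by region will be fitted with study intervention as covariate". SAP 4.2.1.4 makes this the success criterion: "The evidence of efficacy requires a two-sided region-stratified logrank test p-value" of at most 0.10. SAP 4.2.2.4 applies the same test to time to first moderate or severe exacerbation.

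SAP 3.4.1 does not define region. The grouping of 14 countries into four regions appears only in the subgroup lists (SAP 4.2.1.7 and 4.2.3.7). SAP 3.4.1 allows regions with fewer than 10 events to be collapsed, but not how or when. SAP Section 2 does not list the choice of region among the changes to the protocol's analyses, and SAP 4.2.1.5 plans no sensitivity analysis of the primary endpoint.

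**The concern.** If randomisation is blocked within country, the arms have nearly the same country mix, so differences in event risk between countries add almost nothing to the real variability of the treatment comparison. A test that pools several countries in one stratum still counts those differences as noise. Its variance is then too large, and its estimated hazard ratio is pulled somewhat towards 1.

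Power is what is at stake. The design has none to spare: 194 events give just under 80%, and the protocol sets evaluable participants equal to randomised participants (406), with no allowance for dropout. Country differences are plausible. The composite counts antibiotic courses, corticosteroid courses and hospital admissions, and Protocol 8.2.2 lets the setting that counts as an admission vary with the country and its healthcare system.

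**Working it through.** **Inputs from the documents.** Hazard ratio 0.70, two-sided 10% level, 80% power, 194 events, 406 participants, 1:1 allocation, 24-week placebo risk 55% (Protocol 9.2 and 6.3). Regions from SAP 4.2.1.7: North America 2 countries, Eastern Europe 3, Western Europe 6, Rest of the world 3, so 14 in all.

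**The plan's own figure.** Schoenfeld's formula gives 4 × (1.645 + 0.842)² / (ln 0.70)² = 194.4 events. Power at 194 events is Φ(0.3567 × √194 / 2 − 1.645) = Φ(0.839) = 79.9%. The stated sizing reproduces. It uses no strata, so changing the strata leaves the 194 unchanged. The mean per country is 194 / 14 = about 14 events.

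**Simulation.** 406 participants in 14 countries nested in the four regions; 1:1 permuted blocks within country; exponential event times calibrated to 55% placebo risk at 24 weeks; 24 weeks of follow-up. Assumed, because the documents do not give them: blocks of 4, uneven country sizes, and country log-hazards drawn independently with the SD shown and no added regional component. The second column is exp(2 × SD), the hazard ratio between countries one SD above and one SD below the mean.

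| SD | Hazard ratio, +1 vs −1 SD | Type I error: region | Type I error: country | Power: region | Power: country |
|---|---|---|---|---|---|
| 0 | 1.0 | 9.8% | 10.0% | 81.2% | 80.9% |
| 0.25 | 1.6 | 9.7% | 10.1% | 79.3% | 79.5% |
| 0.5 | 2.7 | 8.5% | 9.8% | 76.9% | 79.0% |
| 0.75 | 4.5 | 7.2% | 9.7% | 74.0% | 79.6% |
| 1.0 | 7.4 | 6.6% | 10.8% | 69.9% | 80.5% |

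Monte Carlo standard errors are about 0.3 to 0.4 point for type I error and 0.5 to 0.7 for power. The 10.8% at SD 1.0 is about two standard errors above 10%.

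**Variants at SD 0.5, region against country.** Blocks of 6: type I error 8.7% against 9.9%, power 78% against 80%. Follow-up spread uniformly over 12 to 24 weeks: 9.4% against 10.6%, power 71% against 73%. Power is lower for both in the second variant because only about 163 events accrue.

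**With sparse countries pooled.** A further simulation (4,000 runs per setting) pooled countries with fewer than 10 events within their region. About 10 to 11 strata remained.

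| SD | Type I error: region | Type I error: pooled country | Power: region | Power: pooled country |
|---|---|---|---|---|
| 0 | 9.5% | 9.5% | 80.3% | 80.5% |
| 0.25 | 9.7% | 10.1% | 80.3% | 81.1% |
| 0.5 | 9.1% | 10.0% | 77.9% | 79.2% |
| 0.75 | 7.3% | 9.5% | 75.2% | 79.9% |

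Equal country sizes at SD 0.5 gave type I error 8.1% against 9.6% and power 76.9% against 79.2%. A separate set of runs with the same pooling rule gave power of 81.2% (region) against 80.9% (pooled country) at SD 0, 78.5% against 80.9% at SD 0.5, and 74.5% against 80.3% at SD 0.75.

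**The case against.** Grouping countries into regions is a defensible pre-specified choice in a Phase IIa trial. Country strata would be thin: about 14 events on average, and with uneven sizes 5 or 6 of the 14 countries fall below 10 events. All sites share the same eligibility criteria and event definitions, and neither document gives evidence that country risks differ by the 2.7-fold or more at which the loss shows. A discretionary pooling rule would also add data-dependent choices to the deciding test.

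Part of this stands. The loss is conditional on a spread that nobody can read from the documents, and a pooling rule must be a fixed algorithm. The thin-strata argument does not stand at this size. With no country differences, stratifying by all 14 countries lowers the information in the test only from 49.2 to 48.7, about 1%. With pooling, nearly all the benefit remains at no detectable cost.

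A reader might infer that the region-stratified test fails to control its 10% level. It does control it: in the simulations its type I error was at or below 10% within Monte Carlo error, so no extra false-positive risk arises. A reader might also infer that the randomisation strata are left out altogether. They are not: each region is a set of whole countries, so differences between regions are kept and only differences within a region are lost.

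**Conclusion.** The mismatch is real, unexplained and cheap to remove. The region-stratified test is valid but can be conservative. The power loss is under 1 point at a within-region log-hazard SD of 0.25 or less, about 1 to 3 points at 0.5 and about 5 to 6 points at 0.75. Type I error at SD 0.5 is about 8.5 to 9% in the main runs, and 8.1% to 9.4% across the variants. These sizes rest on the assumed spreads, on blocking within country and on assumed country sizes. Where this trial lies in the range cannot be settled from the documents.

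It would be tempting to extend the point to the repeated-measures and covariance models, where SAP 3.4.3 says "Region will be added as a random effect". The documents do not support that. The calculations here cover the log-rank test only, and the SAP's amendment history records the random region effect as a correction of an error.

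**What to change.** Before unblinding, amend SAP 3.4.1, 4.2.1.4 and 4.2.2.4 as follows.

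- Stratify the log-rank test and the Cox model by country.
- State the region definition in 3.4.1 and replace the discretionary collapse wording with a fixed algorithm run on blinded event counts pooled over the arms: countries with fewer than 10 events are pooled within their region. The algorithm must also say what happens if the pooled remainder still has fewer than 10 events.
- Keep the region-stratified result as a sensitivity analysis.
- List the change in SAP Section 2.

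If the sponsor prefers to keep region as primary, the minimum is to define it in 3.4.1, give the reason, fix the collapse rule and add a country-stratified sensitivity analysis.

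The cost is SAP text, including the pooling algorithm. Sample size, event target and conduct do not change. If countries do not differ at all, the largest power loss seen in any run was 0.5 point (77.5% with region, 77.0% with country).

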3.4.2 Analysis of Covariance (ANCOVA)

The ANCOVA model will be used to fit change from baseline for continuous endpoints collected at only one post-baseline visit. The response variable is the value of the variable of interest at the scheduled post-baseline visit. Region will be added as a random covariate. The

study intervention will be the fixed effect with the baseline value of the variable of interest as covariate. Comparisons of AZD4831 versus placebo will be assessed. The restricted maximum likelihood (REML) approach will be used for the estimation of the variance and covariance parameters of the linear mixed model; two-sided difference test, with alpha level at 10% will be used to compare the difference in means and for the confidence interval calculation. No imputation will be made for missing data.

The reportable results from the model will be:

- The least-squares means (LSmeans) and their standard errors for each study intervention group;
- The difference between AZD4831 and placebo (LSmeans difference) together with its two-sided 90% CI;
- The two-sided p-value for the difference between AZD4831 and placebo.

